5 STUDY POPULATION

Eligibility criteria will be evaluated during the 28-day screening period. Before any study-specific activities/procedures, the appropriate written informed consent must be obtained (see Section 11.1.3). Prospective approval of protocol deviations to recruitment and enrollment criteria, also known as protocol waivers or exemptions, are not permitted.

5.1 Inclusion Criteria

Subjects must meet the following inclusion criteria:

AML-related inclusion criteria for escalation and safety expansion cohort eligibility:

1. AML as defined by World Health Organization (WHO) classification “AML and related neoplasms” in [Arber et al, 2016](#).
2. Disease that is detectable (per Section 8.1.1) after standard first-line therapy, where first-line therapy is defined as:
 - i) attempted remission induction therapy with 1 cycle of anthracycline-based therapy followed by a second cycle for persistent morphologic disease at the first BM assessment; for subjects with CR after 1 cycle followed by early recurrence, a second induction regimen should be considered; OR ii) attempted remission induction with 1 cycle of therapy containing high dose cytarabine; OR iii) hypomethylating agent in combination with venetoclax for at least 2 cycles of therapy;
 - in addition, for eligible subjects in countries where such therapy is approved, an inhibitor must have been attempted for AML with FMS-like tyrosine kinase 3 (FLT3) alterations or isocitrate dehydrogenase (IDH) mutations;
 - in addition, a subject who is considered a candidate for standard-of-care HCT by the investigator must have received transplant prior to study entry.
 - Subjects who have received additional treatment after first-line therapy are eligible, assuming all other entry and exclusion criteria are met.

General Inclusion Criteria:

3. Subjects must be ≥ 18 years of age.
4. Subjects must carry the human leukocyte antigen-A0201 (HLA-A*02:01) allele.
5. Subject must have a projected life expectancy of at least 12 weeks.
6. Subject must have an ECOG performance status of 0 to 1.
7. Subjects must have absolute total lymphocyte count $>200/\mu\text{L}$ within 72 hours of leukapheresis.
8. Subjects must have adequate organ function defined as:
 - Cardiac ejection fraction $\geq 45\%$ without symptoms of cardiac failure or coronary disease
 - Aspartate aminotransferase (AST) $\leq 2.5 \times$ upper limit of normal (ULN) and alanine aminotransferase (ALT) $\leq 2.5 \times$ ULN (unless considered due to leukemic organ involvement).

- Bilirubin $\leq 1.5 \times$ ULN (unless considered due to leukemic organ involvement). Note: Subjects with Gilbert's Syndrome may have a total bilirubin $> 1.5 \times$ ULN but must have direct bilirubin $\leq 1 \times$ ULN.
 - Estimated glomerular filtration rate (eGFR) ≥ 30 mL/min; determined by Chronic Kidney Disease Epidemiology Collaboration (CKD-Epi) Study equation.
9. Subject must voluntarily sign and date an informed consent, approved by an Independent Ethics Committee (IEC)/Institutional Review Board (IRB), prior to the initiation of any screening or study-specific procedures.
10. Subject must agree not to have treatment with another investigational agent for a minimum of 28 days after dosing of NTLA-5001.

5.2 Exclusion Criteria

Subjects must not meet any of the following exclusion criteria:

1. Must not have received prior therapy as follows:
 - Chemotherapy or other targeted antileukemic therapy within 7 days of leukapheresis. Hydroxyurea is permitted up to 72 hours prior to leukapheresis.
 - Hematopoietic growth factors or other immunomodulatory therapy within 7 days of leukapheresis
 - Systemic steroids within 3 days of leukapheresis, except physiologic steroid replacement with ≤ 0.2 mg/kg/day methylprednisolone or equivalent
 - Prior therapy including investigational therapy targeted to WT1 such as vaccine therapy or cell therapy
 - Live vaccine 28 days or fewer prior to planned administration of lymphodepleting therapy
2. Subjects with a history of allogeneic HCT are excluded if:
 - Subjects are less than 84 days post-transplant, or
 - Subjects have evidence of ongoing active graft vs host disease (GvHD) requiring systemic immunosuppressants, or
 - Subjects have received donor lymphocyte infusion (DLI) within 28 days of leukapheresis, or
 - Subjects are on active immunosuppression for GvHD prophylaxis (must be off for 30 days prior to enrollment). Physiologic steroid replacement with ≤ 0.2 mg/kg/day methylprednisolone or equivalent is permitted.
3. [REDACTED]
4. Must not have signs or symptoms indicative of central nervous system (CNS) involvement by tumor. A CNS evaluation should be performed to rule out CNS involvement if indicated by signs or symptoms.
5. Must not have CNS co-morbidity such as transient ischemic attacks, cerebrovascular accident, seizure disorder, or other disorder that could confound neurotoxicity assessments.

6. Must not have severe autoimmunity that has required systemic steroid therapy or other immunomodulatory therapy.
7. Must not have active disseminated intravascular coagulation (DIC), bleeding or coagulopathy during screening.
8. Must be eligible to receive lymphodepleting chemotherapy doses per protocol Section 6.1.3.3
9. Must not have leukocytosis $\geq 20,000$ WBC/ μ L despite hydroxyurea or rapidly progressive disease (e.g., recent increase in blast count above 50%) that in the estimation of the investigator or Sponsor would compromise ability to complete study therapy.
10. Must have recovered from the acute side effects of their prior therapy, such that eligibility criteria are met.
11. Female subjects of childbearing potential are excluded:
 - a. if unwilling to use protocol specified method of contraception (see Section 13.6) during treatment and for an additional 12 months after administration of NTLA-5001.
 - b. who are breastfeeding or who plan to breastfeed during treatment and for an additional 12 months after administration of NTLA-5001.
 - c. with a positive pregnancy test assessed at screening and/or day 0 by a highly sensitive urine or serum pregnancy test.
12. Male subjects with female partners of childbearing potential or female partners who are pregnant are excluded:
 - a. if unwilling to practice sexual abstinence (refrain from heterosexual intercourse) or use a condom during treatment and for an additional 12 months after the last dose of NTLA-5001.
 - b. if unwilling to abstain from donating sperm during treatment and for an additional 12 months after administration of NTLA-5001.
13. Must not have human immunodeficiency virus (HIV) infection, history of Hepatitis B or C infection or positive Hepatitis B surface antigen (HbsAg) or Hepatitis C virus antibody (HCVAb) test, or any uncontrolled infection at screening.
14. Must not have any condition, laboratory abnormality, or other reason that, in the investigator's opinion, could adversely affect the safety of the subject, impair the assessment of study results, or preclude compliance with the study.
15. Must be willing to comply with study procedures including follow-up as specified by the protocol or unwilling to cooperate fully with the investigator.
16. Must not have clinically significant cardiovascular impairment within 12 months of the first dose of study drug, such as history of congestive heart failure greater than New York Heart Association (NYHA) Class II, unstable angina, myocardial infarction, cardiac revascularisation, or cardiac arrhythmia associated with haemodynamic instability.
17. [REDACTED]

5.3 Criteria for Entering the Study Treatment Phase

After leukapheresis, subjects must meet criteria for treatment before lymphodepleting chemotherapy is administered. Criteria for entering the Study Treatment Phase are in Section [8.1.3.1](#).

6 STUDY TREATMENT(S)

6.1 Study Treatment(s) Administered

6.1.1 Investigational Product(s)

NTLA-5001 drug product is a colorless to slightly yellow, clear to slightly cloudy cell suspension. NTLA-5001 will be provided as a [REDACTED] cryobags at variable fill volumes to be stored at $\leq -150^{\circ}\text{C}$ in a liquid nitrogen vapor phase container. The study drug will be thawed at 37°C and the dose will be prepared for infusion by qualified site personnel. Study drug preparation details will be provided in the Cell Therapy Manual. Subjects will receive premedication with anti-pyretic and H1 blocker within 1 hour prior to dosing. NTLA-5001 will be administered as an IV infusion at 10-20 mL/min. Total time from thaw to complete administration may not exceed 4 hours.

The starting dose for NTLA-5001 is [REDACTED] (TCR)-positive viable T cells. Each subject will receive a pre-treatment regimen outlined in Section 6.1.3.1 prior to administration of the study drug.

6.1.2 Comparator Product(s)

This is a single-arm study with no comparator.

6.1.3 Other Protocol-required Therapy

All other protocol-required therapies including, premedications, bridging therapies (if applicable), and lymphodepleting agents, that are commercially available are not provided or reimbursed by Intellia (except if required by local regulation). The investigator or institution will be responsible for obtaining supplies of these protocol-required therapies.

6.1.3.1 Premedication

Subjects will receive premedication with oral anti-pyretic (e.g., acetaminophen 650 mg or equivalent) and H1 blocker (e.g., diphenhydramine 25 mg IV) within 1 hour prior to dosing.

6.1.3.2 Bridging Therapy

Following leukapheresis, subjects may receive bridging therapy with low intensity regimens. Recommended regimens and the washout required prior to lymphodepleting chemotherapy are listed here:

- hydroxyurea (72-hour washout)
- venetoclax (2-week washout)
- azacytidine (2-week washout)
- decitabine (2-week washout)
- cytarabine (2-week washout)

- gilteritinib (4-week washout)
- gentuzumab ozogamicin (4-week washout)
- enasidenib (4-week washout)
- ivosidenib (4-week washout)

To request use of other bridging therapy, the investigator must contact the medical monitor prior to its initiation. Continuation of hydroxyurea during the treatment phase in subjects with morphologic disease may be considered but must be approved by the medical monitor.

6.1.3.3 Lymphodepleting Chemotherapy

Lymphodepleting chemotherapy may be administered in the inpatient or outpatient setting for 3 consecutive days at 24-hour (\pm 3 hours) intervals.

Cyclophosphamide will be administered on Day -5, -4, and -3 as intravenous infusion at 500 mg/m² each day.

Fludarabine will be administered on Day -5, -4, and -3 as intravenous infusion at 30 mg/m² each day.

For chemotherapy dosing, body surface area (BSA) is calculated based on body weight for subjects weighing up to 120% of ideal body weight (IBW), and BSA is calculated based on adjusted body weight for subjects weighing >120% of IBW. IBW and adjusted weight are determined per institutional standard, including the timing of the body weight measurement relative to the chemotherapy dosing. Rounding is permitted per institutional standard.

6.2 Dose Modification

6.2.1 Dose-Cohort Study Escalation, Dose Reduction, and Stopping Rules

6.2.1.1 Dose Escalation Scheme

Proposed Dose Escalation Cohort Number	Planned Dose
Dose Level -1	[REDACTED]
Dose Level 1	[REDACTED]
Dose Level 2	[REDACTED]
Dose Level 3	[REDACTED]

Subjects who enter the treatment group in Arm 1 or in Arm 2 will be assigned to the dose level cohort currently open for enrollment for the relevant Arm. Arm 1 and Arm 2 will be enrolled in parallel.

Up to 3 subjects will be enrolled in an initial dose evaluation group and will be treated with NTLA-5001 for Arm 1 and for Arm 2. Enrollment will be staggered as follows (see figure in Section 13.8):

- Staggering of enrollment across the 2 study Arms: Arm 1 and Arm 2 will be escalated independently. If an Arm 1 subject is dosed at a new dose level before an Arm 2 subject, the Arm 1 subject will be observed through Day 28 before dosing a subject in Arm 2.
- Staggering of enrollment within a dose level cohort (either Arm 1 or Arm 2): each of the first 3 subjects will be observed for 28 days before enrolling the next subject.
- Staggering of enrollment between Dose Levels: all subjects in a dose evaluation group will be observed for 28 days before any subject is enrolled at the next Dose Level.

Once the entire dose evaluation group for a study Arm has been observed for 28 days, all data, including DLT information from all cohorts in both Arms, will be reviewed by the Sponsor and treating investigators to consider dose escalation. The following study personnel must participate in review of the study data and dose escalation decision: the Intellia Medical Lead, the Intellia Safety Lead, and any Investigator who has treated a subject in the cohort that has just completed 28-day observation.

6.2.1.2 Definition of a Dose-limiting Toxicity

DLTs are defined as events with onset within 28 days of infusion as follows:

- Any Grade 4 CRS per American Society for Transplantation and Cellular Therapy (ASTCT) consensus criteria, and Grade 3 CRS that does not resolve to Grade 2 within 72 hours
- Any Grade 3/4 neurotoxicity per ASTCT immune effector cell-associated neurotoxicity syndrome (ICANS) consensus grading criteria for adults
- Any Grade 4 acute GVHD of any duration; Grade 2 or 3 acute GVHD requiring systemic steroid treatment that does not resolve to \leq Grade 1 within 7 days.
- Acute infusion reaction: Reactions related to NTLA-5001 occurring within 2 hours of infusion that are not reversible to \leq Grade 2 within 24 hours.
- Grade 4 neutropenia or thrombocytopenia lasting more than 28 days that is not attributable to underlying disease or lymphodepletion chemotherapy
- Other severe organ toxicity that is not attributable to underlying disease or lymphodepletion chemotherapy as follows: Grade 4 toxicity that is a cardiac disorder, hepatobiliary disorder, renal disorder, respiratory disorder, or vascular disorder (per CTCAE); Grade 3 cardiac, respiratory, or vascular disorder that does not resolve to Grade 2 or lower within 72 hours; or Grade 3 hepatobiliary or renal disorder that does not resolve to Grade 2 or lower within 7 days.
- Grade 5 events without clinical or radiological evidence of disease progression which are related to NTLA 5001.

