6.2.1.3 Dose Escalation and Dose Reduction Decisions

If none of the initial dose evaluation group subjects experience a DLT, subjects in the treatment phase who have not yet received NTLA-5001 and subsequent subjects entering the treatment phase will be eligible for the next dose escalation cohort.

If 1 of the initial dose evaluation group subjects experiences a DLT, enrollment will continue in the dose evaluation group for 3 additional subjects. When the last subject in the expanded dose evaluation group has been observed through Day 28:

- If no subject in the expanded dose evaluation group experiences a DLT, subjects in the treatment phase who have not yet received NTLA-5001 and subsequent subjects entering the treatment phase will be eligible for the next dose escalation cohort.
- If 1 or more additional subject in the expanded dose evaluation group experiences a DLT, no dose escalation will be proposed. Subjects in the treatment phase who have not yet received NTLA-5001 and subsequent subjects entering the treatment phase will be eligible for Dose Level -1 if DLTs are seen at Dose Level 1, or the next lower dose level will be declared the maximum tolerated dose (MTD), if DLTs are seen at Dose Level 2 or 3. Fewer than 2/6 subjects with DLTs will establish the MTD.

If 2 or 3 of the initial dose evaluation group experiences a DLT, no dose escalation will be proposed. Subjects in the treatment phase who have not yet received NTLA-5001 and subsequent subjects entering the treatment phase will be eligible for Dose Level -1 if DLTs are seen at Dose Level 1, or the next lower dose level will be expanded to 6 subjects if DLTs are seen at Dose Level 2 or 3. Fewer than 2/6 subjects with DLTs will establish the MTD.

If a dose escalation is proposed, the subsequent cohort dose may be reduced or increased by up to 50% if the Sponsor and investigator agree, based on observations in the prior cohort. At the Sponsor's discretion, up to 6 subjects may be enrolled in any dose cohort for Arm 1 or Arm 2.

If a subject receiving out-of-specification cells has a DLT, this finding would not be attributed to DLT tally for a specific Dose Level; but would be reviewed as part of the overall safety profile in conjunction with planned safety reviews and by the Sponsor, investigators, and DMC. The event would be considered when making dose escalation decisions, stopping rule decisions, and/or dose selection for expansion cohort.

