6.7.1 Acute Infusion Reaction

Acetaminophen/paracetamol and diphenhydramine /H1 antihistamine may be repeated every 6 hours as needed. If the subject continues to have fever, a course of nonsteroidal anti-inflammatory medication may be prescribed. It is recommended that subjects not receive corticosteroids except in the case of life-threatening emergency, because this may adversely affect NTLA-5001 cells. For additional notes regarding interruption of study drug during an acute infusion reaction, see Section 6.2.3.

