8.5 Adverse Events and Other Safety Aspects

8.5.1 Definition of Adverse Events (AEs)

An AE is defined as any untoward medical occurrence in a subject administered a study drug or has undergone study procedures and which does not necessarily have a causal relationship with this treatment. An AE can therefore be any unintended sign (including an abnormal laboratory finding), symptom, or disease temporally associated with the use of a medicinal (investigational) product, whether or not related to the medicinal (investigational) product.

AEs should be described using a diagnosis whenever possible, instead of individually reporting underlying symptoms. When a clear diagnosis cannot be identified each symptom should be reported as a separate AE.

Some countries may have additional local requirements for events that are required to be reported as AEs or in an expedited manner similar to an SAE. In these cases, it is the investigator's responsibility to ensure these AEs or other reporting requirements are followed and the information is appropriately recorded in the eCRF accordingly.

An abnormality identified during a medical test (e.g., laboratory parameter, vital sign, physical exam) should be defined as an AE only if the abnormality meets 1 of the following criteria:

- Induces clinical signs or symptoms
- Requires active intervention
- Requires interruption or discontinuation of study medication

- The abnormality or investigational value is clinically significant in the opinion of the investigator.

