8.5.2 Criteria for Defining the Severity of an Adverse Event

AEs, including abnormal clinical laboratory values, will be recorded according to the National Cancer Institute (NCI)-CTCAE guidelines (Version 5.0). CRS and ICANS AEs will be recorded according to ASTCT consensus grading (Section 13.5). The items that are not stipulated in the NCI-CTCAE guidelines or ASTCT consensus grading will be assessed according to the criteria in Table 8-1 and entered into the eCRF.

Table 8-1 Criteria for Grading Events Not Stipulated by NCI-CTCAE Guidelines or ASTCT Consensus Grading

Grade	Assessment Standard
1-Mild	Asymptomatic or mild symptoms; clinical or diagnostic observations only; intervention not indicated
2-Moderate	Minimal, local or noninvasive intervention indicated limiting age-appropriate instrumental activities of daily living
3-Severe	Medically significant but not immediately life threatening, hospitalization or prolongation of hospitalization indicated; disabling; limiting self-care activities of daily living
4-Life Threatening	Life threatening consequences, urgent intervention indicated
5-Death	Death related to adverse event

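### A Grade 4 infusion reaction that reverses within 24 hours is a DLT only if another item, such as Grade 4 CRS or organ toxicity, also captures it

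*Protocol*

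**What the plan says.** The infusion-reaction item in Protocol 6.2.1.2 reads "Acute infusion reaction: Reactions related to NTLA-5001 occurring within 2 hours of infusion that are not reversible to" Grade 2 or lower within 24 hours. Relatedness, onset within 2 hours and failure to reverse are its only tests; the peak grade is not one of them.

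The protocol foresees life-threatening reactions. On their management, 6.7.1 says "It is recommended that subjects not receive corticosteroids except in the case of life-threatening emergency". Table 8-1 in 8.5.2, the scale for events outside CTCAE and ASTCT grading, describes Grade 4 as "Life threatening consequences, urgent intervention indicated". Section 7.1 allows the infusion to be stopped for good after a severe reaction.

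The formal escalation rule runs on DLTs alone. In 6.2.1.3 the step up to the next level begins "If none of the initial dose evaluation group subjects experience a DLT". Expansion to 6 subjects, the move to Dose Level -1 and the MTD rule (fewer than 2 of 6 with a DLT) are also stated in DLTs. So is the second condition for simultaneous escalation in 6.2.1.4, which requires that no Arm 1 subject has had a DLT at the current dose.

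A partly dosed subject without a DLT is replaced (4.1.1, 7.1) and is not DLT-evaluable (Protocol Table 9-1, SAP Table 2). A subject with a DLT is evaluable whatever dose was given. SAP 6.1 names DLT incidence as the primary endpoint of the escalation phase.

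**The concern.** The item judges an infusion reaction by how long it lasts and not by how severe it was. A Grade 3 reaction that is still Grade 3 at 25 hours is a DLT, while a Grade 4 reaction that has fallen to Grade 2 by 23 hours is not, under this item. The documents give no reason for treating infusion reactions differently from the other non-haematologic toxicities, and this is a first-in-human trial.

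At stake is whether a related, life-threatening event at a dose level enters the count that decides expansion, de-escalation and the MTD. Whether it does may depend on how the site records it. Section 8.5.1 says "AEs should be described using a diagnosis whenever possible, instead of individually reporting underlying symptoms", which favours a single infusion-reaction entry, and the organ-toxicity item neither names infusion reactions nor excludes them.

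**Working it through.** **1. Each DLT item applied to one event.** Take a Grade 4 event that falls to Grade 2 within 24 hours, with onset inside the 28-day window (Protocol 6.2.1.2).

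| Item | Text on Grade 4 | DLT? |
|---|---|---|
| CRS | "Any Grade 4 CRS per American Society for Transplantation and Cellular Therapy (ASTCT) consensus criteria" | Yes |
| ICANS | any Grade 3 or 4 | Yes |
| GVHD | "Any Grade 4 acute GVHD of any duration" | Yes |
| Organ toxicity | Grade 4 in five named classes, unless due to disease or lymphodepletion | Yes |
| Neutropenia, thrombocytopenia | Grade 4 only if longer than 28 days | No |
| Infusion reaction | no grade named; must fail to reverse in 24 hours | No |

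Cytopenia is the only other Grade 4 item with a duration allowance. Lymphodepletion can itself cause cytopenia, so that allowance has an evident reason.

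**2. Which reactions are left over.** The items are alternatives. A Grade 4 reaction is already a DLT if it is also scored as Grade 4 CRS, as Grade 3 or 4 ICANS, or as a Grade 4 cardiac, hepatobiliary, renal, respiratory or vascular disorder. Only the remaining Grade 4 reactions are exposed.

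**3. What happens to a subject in that subset.**
- Infusion completed and Day 29 assessments done: evaluable, counted as DLT-free.
- Infusion stopped: replaced and outside the DLT Evaluable Set.

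**4. Worked example at Dose Level 1.** Five subjects are dosed. Two have such a reaction and the infusion is stopped; three complete without a DLT.
- As written: 0 DLTs in 3 evaluable subjects, so the formal rule permits the next level.
- If Grade 4 counted: 2 DLTs, no escalation, Dose Level -1. This holds in any dosing order. Subject 5 is the third completer, so subjects 1 to 4 include both reactions, and subjects 1 to 3 include one or two of them. With two, the cohort stops at once. With one, it expands, and subject 4 is the second DLT.

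**5. Size over a range of rates.** The documents state no rate and no figure to reproduce. Let r be the assumed probability, per dosed subject, of a reaction in the exposed subset. With no other DLTs, the formal rule as written passes the dose level with probability 1 at every r. If these reactions counted, under the 3+3 rule in 6.2.1.3:

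P(pass) = (1 − r)³ + 3r(1 − r)² × (1 − r)³ = (1 − r)³ + 3r(1 − r)⁵

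| r | (1 − r)³ | 3r(1 − r)⁵ | P(pass) if counted | P(pass) as written |
|---|---|---|---|---|
| 0.05 | 0.857 | 0.116 | 0.973 | 1 |
| 0.10 | 0.729 | 0.177 | 0.906 | 1 |
| 0.20 | 0.512 | 0.197 | 0.709 | 1 |
| 0.30 | 0.343 | 0.151 | 0.494 | 1 |

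**6. With other DLTs present.** Assume a 10% rate of all other DLTs, independent of r, so the total rate is 1 − 0.9(1 − r). P(pass) is then 0.906 as written, against 0.824, 0.730, 0.536 and 0.360 if the reactions counted, at the same four values of r.

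**The case against.** A reader might infer that every reversible Grade 4 infusion reaction escapes the tally. The documents do not support that. Section 6.7.2 makes fever with positive-pressure ventilation or multiple vasopressors Grade 4 CRS, and a Grade 4 respiratory, cardiac or vascular event meets the organ item. Section 8.5.1 governs how AEs are described and does not take such an event out of that item. This objection stands, which is why r covers only the leftover subset. That subset may be small.

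A reader might also infer that escalation would follow automatically. It would not. Section 6.2.1.1 requires a review of all data after 28 days, with the medical lead, the safety lead and the treating investigators taking part. A severe reaction must be discussed with the medical monitor before the infusion resumes (6.2.3). The sponsor may enlarge a cohort to 6 or reduce the next dose by up to 50% (6.2.1.3), and the DMC may be consulted at any time. All of this stands. But the same review would see Grade 4 CRS, which the protocol still makes a binding DLT.

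A third inference would be that the pausing criteria in 6.2.1.5 repeat the gap because they do not name infusion reactions. They show no such contrast: Grade 4 CRS or ICANS that resolves to Grade 1 within 72 hours does not pause enrollment either.

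Nor would the event go unreported. Safety by AEs is also a primary endpoint (Protocol 3, SAP 2.1). SAP 6.5.1 counts Grade 4 TEAEs, AEs of special interest, and TEAEs leading to infusion interruption or discontinuation. Only the DLT flag would be missing.

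Finally, the item may be called a design preference. The thresholds in the list do differ by toxicity, and infusion reactions are a known effect managed by premedication and by slowing or stopping the infusion. A reversibility test suits Grade 3. The documents give no reason for applying it to a life-threatening reaction.

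**Conclusion.** The concern holds for a defined subset: related Grade 4 infusion reactions that reverse to Grade 2 or lower within 24 hours and are not also scored under another DLT item. For these, the formal count stays at zero, and nothing in the expansion, de-escalation, MTD or simultaneous-escalation rules responds. Protection then rests on judgement.

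The size depends wholly on an assumed rate. With no other DLTs, counting these reactions lowers the chance of passing a dose level by 0.03, 0.09, 0.29 and 0.51 at r = 0.05, 0.1, 0.2 and 0.3. These figures do not describe Grade 4 infusion reactions as a whole.

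SAP section 7 says that 2 subjects received NTLA-5001 before termination, and the documents do not say whether either had an infusion reaction. The point therefore concerns the rule as written and any reuse of it. It is a cheap improvement in safety and consistency; it does not invalidate the design.

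**What to change.** Reword the infusion-reaction bullet in Protocol 6.2.1.2 so that a DLT is any Grade 4 infusion reaction related to NTLA-5001, of any duration, or a Grade 3 reaction that does not return to Grade 2 or lower within 24 hours. Keep the 2-hour onset window. Section 4.1.1, Protocol Table 9-1 and SAP Table 2 need no change, because a subject with a DLT is already evaluable at any dose received.

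If the sponsor wants to keep the exemption, state the reason and say whether a Grade 4 organ event within an infusion reaction counts under the organ item.

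The drafting cost is a few words. The operating cost is that a reversible Grade 4 reaction could expand a cohort or stop escalation. At r = 0.2 with no other DLTs, a dose level would fail about 29% of the time (1 − 0.709), and failure at Dose Level 1 means Dose Level -1. The 3+3 rule already imposes that same cost for any other DLT occurring at that rate.
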